9.5. ECOG Performance Status

The number and percentage of patients with each ECOG status will be summarized at scheduled visits. All ECOG data will be presented in a listing.

10. Pharmacodynamics and Biomarker Analysis

Summary of the number and percentage of patients with screening status and confirmatory status of presence of anti-OX40L, the screening and confirmatory status of the presence of anti-polyethylene glycol (PEG), as well as the titer information of anti-OX40L and anti-PEG will be summarized by visit based on the safety set for treatment arm and dose cohort (as specified in [Section 3.3](#)) for Phase I and Phase II, and total for each treatment arm combining Phase I and Phase II.

All pharmacodynamic data will be presented in listings based on the safety set.

Tumor biopsies will be examined using quantitative immunofluorescence (QIF) and/or an orthogonal method (i.e. enzyme-linked immunosorbent assay [ELISA]) for changes in OX40L/OX40 and PD-L1/PD-1 expression levels, as well as characterization of tumor infiltrating lymphocyte populations (e.g., phenotype, distribution, and activation). Descriptive statistics for each parameter may be provided for observed values and change from baseline values by scheduled visit, treatment arm, dose cohort, and total, and biopsy cohort group for Phase I, and by scheduled visit, treatment arm, dose cohort, and biopsy cohort group for Phase II based on the safety set.

All biomarker data will be presented in listings. Biomarker data (summary table and listing) will be provided in the Biomarker Report.

11. Pharmacokinetic Analysis

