7.3 SECONDARY OBJECTIVES

The secondary objectives of the study are as follows:

- To assess emergence of antibodies against the drug product as well as OX40L, the protein translated by the drug product
- To assess mRNA pharmacokinetics (PK) alone and in combination with durvalumab
- To assess anti-tumor effects of mRNA-2416 alone and in combination with durvalumab
- Phase I only: To assess objective response rate and duration of response of mRNA-2416 monotherapy based on Response Evaluation Criteria in Solid Tumors (RECIST) v1.1 / or Cheson 2014 criteria (lymphomas)

- Phase II only: To assess disease control rate and duration of response of mRNA-2416 alone and in combination with durvalumab based on Response Evaluation Criteria in Solid Tumors (RECIST) v1.1

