13.4.4 PK AND PHARMACODYNAMIC ANALYSES

mRNA-2416 and durvalumab PK parameters to be determined will include, but are not limited to, Cmax, time to maximum observed concentration, elimination half-life, and AUC. Where possible, descriptive statistics of the PK parameters will be provided; individual patient mRNA-2416 concentrations, actual sampling times, and PK parameters will be listed.

This study will assess the immunological effects of each treatment cycle on the cellular and humoral immune responses in the peripheral circulation and in tumor biopsy specimens. Humoral immune responses (potential antibody production) to the study drug will be compared to baseline in serum samples.

Tumor biopsies will be examined using immunohistochemistry, qualitative immunofluorescence and/or an orthogonal approach (i.e. ELISA) for changes in OX40L/OX40 and PD-L1/PD-1 expression levels, as well as characterization of tumor infiltrating lymphocyte populations (eg, phenotype, distribution, and activation). Plasma may be evaluated for changes in cytokine levels.

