In addition to the information presented in the statistical methods section of the protocol (Section 13) which provides the principal features of planned analyses for this study, this SAP provides appropriate statistical analysis methodologies in details. It also documents modifications or additions (if applicable) to the analysis plan that are not “principal” in nature and result from information that was not available at the time of protocol finalization.

PPD Biostatistics and Programming team, designee of Moderna Biostatistics and Programming department, will perform the statistical analysis of the efficacy, safety, pharmacokinetic, and pharmacodynamics; Statistical Analysis System (SAS) Version 9.4 or higher will be used to generate all statistical outputs (tables, figures, listings, and datasets). The SAP will be finalized and approved prior to the clinical database lock for primary analysis. If the methods in this SAP differ from the methods described in the protocol, the SAP will prevail.

2. Study Objectives

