2.2. Secondary Objectives

The secondary objectives of the study are as follows:

- To assess emergence of antibodies against the drug product as well as OX40 ligand (OX40L), the protein translated by the drug product
- To assess mRNA PK alone and in combination with durvalumab
- To assess anti-tumor effects of mRNA-2416 alone and in combination with durvalumab
- Phase I only: To assess objective response rate and duration of response (DOR) of mRNA-2416 alone and in combination with durvalumab based on RECIST v1.1 or Cheson 2014 criteria (lymphomas)
- Phase II only: To assess disease control rate (DCR) and DOR of mRNA-2416 alone and in combination with durvalumab based on RECIST v1.1

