3.2.2. Secondary Endpoints

The secondary endpoints of the study are as follows:

- Presence and/or concentration of antibodies against the drug product as well as OX40L, the protein translated by the drug product
- Phase I only: Assessment of objective response rate, DOR, and progression-free survival (PFS) of mRNA-2416 alone and in combination with durvalumab based on RECIST v1.1 or Cheson 2014 criteria (lymphomas)

- Phase II only: Assessment of DCR, DOR, and PFS of mRNA-2416 alone and in combination with durvalumab in patients with ovarian cancer based on RECIST v1.1
- PK parameters for mRNA-2416 alone and in combination with durvalumab: maximum observed concentration (C_{max}) and area under the concentration-time curve (AUC)

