Unless otherwise specified, the first/last dose refers to the first/last dose of study drug (mRNA-2416 or durvalumab). Study day for events on or after the date of the first dose will be defined as the number of days from the date of the first dose, plus 1 day, so that the date of the first dose will be defined as Day 1. For events before the date of the first dose, study day will be calculated as the difference in days between the date of the first dose and the date of interest. Thus, the day before the date of the first dose will be defined as Day -1. This means there will be no study Day 0.

Baseline is defined as the last assessment prior to the first dose. All baseline measurements must have been collected prior to administration of the first dose. Measurements obtained after the first dose will be considered as post-baseline values. If the measurement of a variable is not made on a given patient prior to the first dose, that patient will be considered not to have a baseline value for that variable. Change from baseline is defined as post-baseline assessment minus baseline assessment.

Continuous data will be described using the following descriptive statistics: the number of patients (n), mean, standard deviation, median, minimum and maximum, where appropriate. Categorical data will be summarized using the frequency count (n) and percentage (%) of patients for each category, where appropriate. Percentages will be based on non-missing data unless specified otherwise.

Unless otherwise specified, all statistical tests will be 2-sided and conducted at the 0.05 significance level.

No imputation will be applied for missing data unless otherwise specified.

All collected data used for safety and efficacy evaluations will be presented in listings. Data will be displayed in all listings sorted by treatment arm, cohort (dose escalation/confirmation/expansion), dose cohort, and patient identifier unless otherwise specified.

The Medical Dictionary for Regulatory Activities (MedDRA) will be used for coding AEs and medical histories. Prior or concomitant medication data will be coded using the World Health Organization (WHO) Drug Dictionary.

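### The objective is emergence of antibodies, but the SAP tabulates only status and titer by visit, which does not give the number of patients who convert

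*SAP*

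**What the plan says.** Protocol Section 7.3 lists as a secondary objective: "To assess emergence of antibodies against the drug product as well as OX40L, the protein translated by the drug product". SAP Section 2.2 repeats it almost word for word: "To assess emergence of antibodies against the drug product as well as OX40 ligand (OX40L), the protein translated by the drug product". The matching endpoint in SAP Section 3.2.2 (and Protocol Section 7.4) does not mention emergence: "Presence and/or concentration of antibodies against the drug product as well as OX40L, the protein translated by the drug product".

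On analysis, Protocol Section 13.4.4 states: "Humoral immune responses (potential antibody production) to the study drug will be compared to baseline in serum samples".

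SAP Section 10 plans the "number and percentage of patients with screening status and confirmatory status of presence of anti-OX40L", the same for anti-PEG, and "titer information of anti-OX40L and anti-PEG will be summarized by visit based on the safety set", by arm and dose cohort. Here screening status most naturally means the first assay tier, not the screening visit. All pharmacodynamic data also go into listings.

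Two general rules bear on this. SAP Section 4 says "Percentages will be based on non-missing data unless specified otherwise" and imputes nothing by default. SAP Section 1 says "If the methods in this SAP differ from the methods described in the protocol, the SAP will prevail".

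The samples for a baseline comparison exist. Protocol Table 6 schedules immunogenicity sampling pre-dose on Cycle 1 Day 1, on Cycle 1 Day 15, at Cycle 2 Day 1, at several visits from Cycle 3 to Cycle 6, and at end of treatment.

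**The concern.** Emergence is a change within a patient: negative before treatment and positive after, or positive before and clearly higher after. A table of counts by visit holds one total per visit. It does not link a patient's baseline result to the later ones.

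SAP Section 10 defines no baseline-negative denominator, no shift from baseline, no titer rise that counts as a boost, and no summary of patients positive at any post-baseline time. Elsewhere the SAP asks for change from baseline by name: hematology (9.2.1), vital signs (9.3), ECG (9.4), and biopsy markers in Section 10 itself. SAP Section 9 names anti-drug antibodies among the safety evaluations but gives no method. SAP Section 13 lists one change from the plan, the dropped correlation endpoint, and does not mention the baseline comparison.

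At stake is whether the report can say how many patients developed antibodies. The question is not idle: Protocol Section 6.2 reports that every animal treated with mRNA-2416 developed an anti-human-OX40L response and that patients may seroconvert.

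**Working it through.** The documents give no sample size, error rate or expected rate for the antibody analysis, so there is no planned figure to reproduce. The check asks what the planned table can determine.

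**Inputs.** N = 27 and N = 41 are the evaluable targets for the Arm A and Arm B expansions (SAP Section 4.1). The number positive at baseline (b), the number positive at a later visit (v) and the pattern of departures are assumptions.

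**1. Conversions from two row totals, with everyone sampled at both visits.** The baseline-negative patients number N − b. Among them, the number positive at the later visit lies between

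- lower limit: max(0, v − b), when every baseline-positive patient stays positive;
- upper limit: min(v, N − b), when as many baseline-positive patients as possible have reverted.

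| N | b | v | Induced, lowest | Induced, highest |
|---|---|---|---|---|
| 27 | 0 | 11 | 11/27 = 40.7% | 11/27 = 40.7% |
| 27 | 5 | 11 | 6/22 = 27.3% | 11/22 = 50.0% |
| 27 | 11 | 11 | 0/16 = 0% | 11/16 = 68.8% |
| 41 | 8 | 16 | 8/33 = 24.2% | 16/33 = 48.5% |

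With no baseline positives the table determines conversions at that visit exactly. Once some patients are positive at baseline, it gives only a range.

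**2. Early departure.** Take N = 27, all negative at baseline, with 10 converting early and staying positive: 10/27 = 37.0%.

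- If 70% of converters and 30% of the other 17 leave, 3 and about 12 remain. A late row shows 3/15 = 20.0% of those sampled, or 3/27 = 11.1% if the safety set is the denominator.
- If 30% of converters and 70% of the others leave, 7 and about 5 remain: 7/12 = 58.3%.
- If half of each group leaves, 5 and 8 or 9 remain: 5/13 = 38.5% or 5/14 = 35.7%, close to the true 37.0%.

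On a non-missing denominator the late row is therefore off materially only when leaving is related to antibody status. On a safety-set denominator any converter who leaves lowers it. SAP Section 10 names the safety set and Section 4 makes non-missing data the default, so the denominator is not settled.

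**3. Which rows a leaver appears in.** A patient who converts at Cycle 1 Day 15 and stops during Cycle 2 is due samples at Cycle 1 Day 15, Cycle 2 Day 1 and end of treatment. That patient is absent from the scheduled rows from Cycle 3 on, not from all later rows.

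**The case against.** The strongest reply is that the SAP table delivers the endpoint. Presence is the assay status and concentration is the titer. The mismatch between objective and endpoint already lies within the protocol (Sections 7.3 and 7.4). A by-visit table should show the pre-dose Cycle 1 Day 1 row, so baseline positivity is visible in aggregate, and if baseline positives stay positive, the rise over baseline is the number of conversions. The listings let a reader trace individual patients, which is easy in escalation cohorts of 3 to 6. No test, dose rule or stopping rule uses a tabulated antibody incidence.

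All of that stands. It limits the point to a missing summary, with no data lost. It does not supply the summary: persistence of baseline positivity cannot be assumed, and reading conversions from listings without a prespecified definition leaves the definition to be chosen after the results are seen.

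A reader might infer more, and the documents do not support it:

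- That the SAP's precedence clause cancels the protocol's baseline comparison. The protocol sentence names no particular statistic, and the SAP leaves the comparison unspecified without excluding it.
- That the report will overstate emergence by counting pre-existing positives. The SAP nowhere labels a by-visit percentage as emergence.
- That pre-existing antibodies, anti-PEG in particular, are common here. The documents give no baseline rate for either antibody.
- That patient safety is at issue. Protocol Section 6.2 does not anticipate significant risk from seroconversion in patients.

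**Conclusion.** The point holds as a gap between the objective and the planned summary. SAP Section 10 meets the endpoint wording but cannot report how many patients developed or boosted antibodies on treatment, which is what both documents set out to assess.

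Its size depends on figures the documents do not contain. With 5 of 27 positive at baseline and 11 of 27 later, the planned table leaves treatment-induced incidence anywhere between 27% and 50%. With no baseline positives and complete sampling it leaves no uncertainty about conversions at that visit. Early departure adds to the problem in later scheduled rows, and the end-of-treatment sample offsets this in part. No efficacy conclusion, sample size or error rate is affected.

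**What to change.** In SAP Section 10, for anti-OX40L and anti-PEG separately, add one per-patient summary by arm and dose cohort, among patients with a baseline and at least one post-baseline result:

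- **Baseline positive:** number and percentage.
- **Treatment-induced:** baseline negative and confirmed positive at any post-baseline time, including end of treatment, as a percentage of baseline-negative patients.
- **Treatment-boosted:** baseline positive with a titer rise above a threshold fixed in advance from the assay's validation, as a percentage of baseline-positive patients.

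Keep the by-visit table as supportive and state its denominator: patients sampled at that visit, or the safety set. Footnote the number of patients without a baseline sample, since they cannot enter the new summary.

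The cost is one derived status per antibody and one table, from samples already scheduled. No added visits, samples or patients are needed.

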10.13.3 DOSE EXPANSION BIOPSY COLLECTION PLAN

For all patients in dose expansion, collection of newly obtained tumor samples during screening and at 1 of the time points as specified below is required unless not medically feasible and agreed by the Sponsor. An additional optional biopsy at the time of treatment response or disease progression is also requested if medically feasible.

For all patients in dose expansion, biopsies at screening should be performed on a lesion which is planned for injection of study treatment, as well as a distal non-visceral lesion which is not planned for injection of study treatment if medically feasible. Similarly, the on-treatment biopsies should be performed on a lesion which has been injected with study treatment, as well as on a distal non-visceral lesion which has not been injected with study treatment if medically feasible. Every attempt should be made to biopsy the same injected and distal lesions at all time points.

Patients in dose expansion will be assigned to biopsy groups which each have a different timepoint for the on-treatment biopsies, as specified below.

Arm A Expansion Biopsy Group D:

Within 14 days pre-dose Cycle 1 Day 1: A baseline tumor biopsy of a lesion that is planned for intratumoral injection, as well as a distal non-visceral lesion which is not planned for injection if medically feasible.

24 to 48 hours post-dose Cycle 1 Day 1: Tumor biopsy of the injected tumor lesion, as well as a distal non-visceral lesion which has not been injected with study treatment if medically feasible. The biopsy of the injected lesion should include or be as close as possible to the injection site.

Arm A Expansion Biopsy Group E:

Within 14 days pre-dose Cycle 1 Day 1: A baseline tumor biopsy of a lesion that is planned for intratumoral injection, as well as a distal non-visceral lesion which is not planned for injection if medically feasible

Pre-dose Cycle 2 Day 1: Tumor biopsy of the injected tumor lesion, as well as a distal non-visceral lesion which has not been injected with study treatment if medically feasible. The biopsy of the injected lesion should include or be as close as possible to the injection site.

Arm B Expansion Biopsy Group F:

Within 14 days pre-dose Cycle 1 Day 1: A baseline tumor biopsy of a lesion that is planned for intratumoral injection, as well as a distal non-visceral lesion which is not planned for injection if medically feasible.

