24 to 48 hours post-dose Cycle 1 Day 1: Tumor biopsy of the injected tumor lesion, as well as a distal non-visceral lesion which has not been injected with study treatment if medically feasible. The biopsy of the injected lesion should include or be as close as possible to the injection site.

Arm B Expansion Biopsy Group G:

Within 14 days pre-dose Cycle 1 Day 1: A baseline tumor biopsy of a lesion that is planned for intratumoral injection, as well as a distal non-visceral lesion which is not planned for injection if medically feasible

Pre-dose C1D15: Tumor biopsy of the injected tumor lesion, as well as a distal non-visceral lesion which has not been injected with study treatment if medically feasible. The biopsy of the injected lesion should include or be as close as possible to the injection site.

Arm B Expansion Biopsy Group H:

Within 14 days pre-dose Cycle 1 Day 1: A baseline tumor biopsy of a lesion that is planned for intratumoral injection, as well as a distal non-visceral lesion which is not planned for injection if medically feasible

Pre-dose Cycle 2 Day 1: Tumor biopsy of the injected tumor lesion, as well as a distal non-visceral lesion which has not been injected with study treatment if medically feasible. The biopsy of the injected lesion should include or be as close as possible to the injection site.

Table 8: Arm A Dose Expansion Tumor Biopsy Analyses by Group

Group	Biopsy Timing	Biopsy Sites	Analyses	
			OX40/OX40L Expression	Additional Tumor Microenvironment Characterization by IHC/ QIF and/or RNAseq
D	First biopsies: Within 14 days pre-study (C1D1)	1) Lesion planned for injection of study drug 2) Lesion NOT planned for injection of study drug	X	X
	Second biopsies: 24-48 hrs after C1D1 injection	1) Lesion injected with study drug 2) Lesion NOT injected with study drug	X	X
E	First biopsies: Within 14 days pre-study (C1D1)	1) Lesion planned for injection of study drug 2) Lesion NOT planned for injection of study drug	X	X
	Second biopsies: Pre-dose C2D1 injection	1) Lesion injected with study drug 2) Lesion NOT injected with study drug	X	X

OX40L=OX40 ligand; QIF= quantitative immunofluorescence; RNAseq= RNA sequencing

Table 9: Arm B Dose Expansion Tumor Biopsy Analyses by Group

Group	Biopsy Timing	Biopsy Sites	Analyses	
			OX40/OX40L Expression	Additional Tumor Microenvironment Characterization by IHC/ QIF and/or RNAseq

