Listings will be provided for tumor assessment of target lesions, non-target lesions, new lesions, and overall response evaluation. Waterfall plots of best percent change from baseline in sum of diameters of target lesions based on investigator assessments (per RECIST 1.1 and irRC, respectively) will be provided by treatment arm, and by treatment arm and injection status, respectively.

The following efficacy endpoints will be analyzed:

- ORR based on RECIST 1.1/Cheson 2014 criteria
- ORR based on irRC/LYRIC
- DOR based on RECIST 1.1/Cheson 2014 criteria
- PFS based on RECIST 1.1/Cheson 2014 criteria
- PFS based on irRC/LYRIC
- DCR based on RECIST 1.1

All derived efficacy parameters will be displayed in a data listing.

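### SAP 10 has no lesion factor and SAP 4 no same-lesion baseline, so Phase II biopsy summaries produced as written would mix injected and distal lesions

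*SAP*

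**What the plan says.** Protocol 10.13.3 asks each expansion patient for a screening biopsy of a lesion chosen for injection, "as well as a distal non-visceral lesion which is not planned for injection of study treatment if medically feasible". Later in treatment, "the on-treatment biopsies should be performed on a lesion which has been injected with study treatment, as well as on a distal non-visceral lesion", again with a feasibility condition on the distal one. Tables 8 and 9 carry this through: for each of Groups D to H the on-treatment entry reads "1) Lesion injected with study drug 2) Lesion NOT injected with study drug", with the Group H entry adding that each should be the lesion sampled at baseline. What defines the groups is timing: "Patients in dose expansion will be assigned to biopsy groups which each have a different timepoint for the on-treatment biopsies".

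SAP 10 says that descriptive statistics of observed values and of change from baseline may be given for each biopsy parameter, for Phase II "by scheduled visit, treatment arm, dose cohort, and biopsy cohort group for Phase II based on the safety set". The tables and listings are to appear in a separate Biomarker Report.

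The only baseline rule is the general one in SAP 4: "Baseline is defined as the last assessment prior to the first dose". It is framed per patient and per variable.

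Injection status is used elsewhere in the SAP. The waterfall plots in SAP 8 are to be drawn "by treatment arm, and by treatment arm and injection status, respectively".

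**The concern.** The biopsies serve two questions. One is whether the drug raises OX40L expression where it is injected. The other is whether immune cells also enter lesions that were not injected. In Phase I the biopsy group keeps these apart, because Group A samples uninjected lesions and Groups B and C sample injected ones (Protocol 10.13.2). In Phase II each group contains both lesion types, yet SAP 10 relies on the same group factor.

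Two things are at stake. A mean over both lesion types dilutes a local effect and cannot show a distal one. A change computed from one lesion's baseline to another lesion's on-treatment value brings in the between-lesion variation that Protocol 10.13.1 sets out to limit. Because the distal biopsy depends on feasibility, the mix of lesions may also vary between biopsy groups or between arms, and a difference in mix could be read as a difference in effect.

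**Working it through.** The plan states no figure for this analysis, so there is none to reproduce. The check is first a reading of the text, then an illustration with assumed inputs.

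**1. Does any Phase II factor identify the lesion?**

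| Factor in SAP 10 | What it separates in Phase II | Separates injected from distal? |
|---|---|---|
| Scheduled visit | screening, on treatment | No; both lesions are sampled at both |
| Treatment arm | A (Groups D, E), B (Groups F, G, H) | No |
| Dose cohort | mRNA-2416 dose | No |
| Biopsy group | time of the on-treatment biopsy | No; each of D to H has both lesions |

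A patient who gives both samples therefore has two values of the same parameter in one cell.

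**2. What does the baseline rule select?** Protocol 10.13.3 places the screening biopsies within 14 days before Cycle 1 Day 1 and does not say that both are taken on one day.

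- On different days, the rule read literally picks the later sample, whichever lesion it came from, as the patient's baseline.
- On the same day, it does not say which of the two values is baseline.
- If the lesion sampled before dosing cannot be injected, Protocol 10.13.1 lets another lesion be injected, provided it can be biopsied afterwards. That lesion may have no pre-dose sample. The SAP has no rule for this.

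**3. How much could a local change be diluted?** Let f be the share of patients with a distal sample and r the distal change divided by the local change. The documents give neither. With one injected record per patient and every record weighted equally:

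pooled change / local change = (1 + f·r) / (1 + f)

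| f | r = 0 | r = 0.5 |
|---|---|---|
| 0.25 | 1/1.25 = 80% | 1.125/1.25 = 90% |
| 0.50 | 1/1.50 = 67% | 1.25/1.50 = 83% |
| 0.75 | 1/1.75 = 57% | 1.375/1.75 = 79% |
| 1.00 | 1/2.00 = 50% | 1.50/2.00 = 75% |

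If the two values were averaged within patient first, the ratio would be 1 − f·(1 − r)/2. For r = 0 that is 87.5%, 75%, 62.5% and 50%. Dilution is absent only when r = 1.

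The table also shows the effect of lesion mix. With r = 0 and an identical local change, a group with f = 0.25 would report 80% of it and a group with f = 0.75 would report 57%.

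**4. What would a cross-lesion change cost in precision?** Take a value as patient plus lesion plus error, with lesion effects independent and s the lesion share of the within-patient variance (assumed). Scaling that variance to 1, the variance of change is 2(1 − s) within a lesion and 2 across lesions. The SD ratio is √(1/(1 − s)): 1.15, 1.41 and 2.0 for s = 0.25, 0.50 and 0.75. Any systematic difference between the two lesions at screening would be added to the apparent change.

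**The case against.** The strongest reply is that the SAP is silent on lesions rather than wrong about them. It never tells the analyst to combine lesions, it makes the summary optional, and it sends the output to a Biomarker Report that is not among the documents and may well separate them. All of the data are to be listed. The protocol asks that every effort be made to sample the same lesions each time, so a sensible analyst would pair by lesion. The endpoint is exploratory, and Protocol 10.13 describes biomarker data as supportive and lets the sponsor drop assessments.

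Much of this stands. A reader might infer that the plan orders pooling; it does not, and the point is only what would follow if its listed factors and baseline rule were applied as they are. A reader might also infer that patients with two samples would be counted twice in n. SAP 4 defines n for continuous data as the number of patients, so that is not supported; what is missing is a rule for the second value.

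The rest does not remove the gap. The optional wording decides whether a table is made, not how it is built. The protocol's aim of sampling the same lesion governs collection, not the choice of baseline value in the analysis. Since the SAP already splits the waterfall plots by injection status, the distinction is one that the sponsor regards as worth showing.

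**Conclusion.** The point holds conditionally. None of the four factors listed for the Phase II biopsy summaries separates an injected from a distal lesion, and the only baseline rule has no lesion level. Produced as written, the summaries would put both lesion types in one cell and could take change across lesions or leave baseline undefined.

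The size is illustrative. Over the assumed ranges in the table the reported change is 50% to 90% of the local change, with equal weight per record. A reader might infer that a local effect would simply be halved. That needs a distal sample from every patient and no distal change at all. The feasibility condition, and the eligibility rule that allows for patients with a single lesion suitable for injection, biopsy and RECIST assessment (Protocol 9.1, criterion 4c), make complete pairing unlikely. How often the screening biopsies fall on different days, or lesions are switched, is not stated either, so the frequency of cross-lesion changes is unknown.

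The consequence is confined to the exploratory tumour-tissue endpoints. The primary objective response rate, the two-stage designs and the sample size do not use these summaries.

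**What to change.** In SAP 10, and in the specification of the Biomarker Report:

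- add injection status (injected, non-injected) to the factors for the Phase II biopsy summaries, within visit, arm, dose cohort and biopsy group;
- define baseline for biopsy parameters as the last pre-dose biopsy of the same lesion;
- list pairs that come from different lesions separately, outside the change-from-baseline summaries.

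The sponsor should confirm that lesion identity and injection status are recorded for each biopsy sample. Protocol Tables 8 and 9 imply it, but the case report form is not available here, so it should not be taken as given.

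The cost is a wording change. The drawback is fewer patients per cell in groups that are already small, and some loss of data from mismatched pairs. Where cells become too thin to summarise, the listings by lesion can carry the result.
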